7.3.4 Veri Strat® Assay Schedule

- Baseline visit (pre-treatment)
- Cycle 3 Day 1 visit (prior to treatment)
- At disease progression

CONFIDENTIAL

STUDY DRUG(S): EVEROLIMUS
FINAL PROTOCOL DATE: 19 JUNE 2014

SCRI INNOVATIONS STUDY NUMBER: BRE 212
VERSION 1.0

- At the first Follow-Up visit after disease progression

7.4 Response Assessment Every 2 Cycles

Patients will be reevaluated for response to treatment after every 2 cycles of treatment, prior to the start of odd-numbered cycles. The following assessments will be performed:

- CT scans of chest
- CT of abdomen and pelvis
- Bone scan (if abnormal at baseline)

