Anti-estrogen Therapy (tamoxifen, fulvestrant, anastrozole, letrozole, exemestane, toremifene, or LHRH agonist in conjunction with anti-estrogen therapy)

The patient will be prescribed the last anti-estrogen therapy to which they demonstrated disease progression. Anti-estrogen therapy (tamoxifen, fulvestrant, anastrozole, letrozole, exemestane, toremifene, or LHRH agonist in conjunction with anti-estrogen therapy) will be administered according to the directions in the FDA approved labeling. Consult the appropriate package insert for specific information and instructions.

Restaging

A treatment cycle will be defined as 4 weeks, with radiological evaluations every 2 cycles (8 weeks). Patients will be evaluated for response to treatment before every odd numbered cycle with imaging and chemistry. Patients will be treated until disease progression, toxicity requiring cessation of treatment or withdrawal of consent.

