6.1 Dose Modifications Due to Hematologic Toxicity

Dose modifications on Day 1 of each cycle will be based on blood counts determined on the day of scheduled treatment. Nadir blood counts will not be used to determine dose modifications. Treatment on Day 1 of any cycle will proceed if blood counts demonstrate ANC $\geq 1.5 \times 10^9/L$ and platelets $\geq 100 \times 10^9/L$ (See Table 2).

CONFIDENTIAL

STUDY DRUG(S): EVEROLIMUS
FINAL PROTOCOL DATE: 19 JUNE 2014

SCRI INNOVATIONS STUDY NUMBER: BRE 212
VERSION 1.0

Table 2 Everolimus Dose Modifications Due to Hematologic Toxicities

Toxicity	Actions
Grade 3 thrombocytopenia (platelets <50, $\geq 25 \times 10^9/L$)	Interrupt everolimus until resolution to \leq Grade 1. If AE resolution occurs \leq 7 days, reintroduce everolimus at the dose level prior to interruption. If AE resolution occurs $>$ 7 days, or event recurs within 28 days, reintroduce everolimus at one dose level lower, if available.
Grade 4 thrombocytopenia (platelets < $25 \times 10^9/L$)	Interrupt everolimus until recovery to \leq Grade 1. Then reintroduce everolimus at one dose level lower, if available.
Grade 3 Neutropenia (neutrophils $<1, \geq 0.5 \times 10^9/L$) or Grade 3 anemia (Hgb <8.0-6.5g/dL; <4.9-4.0 mmol/L; <80-65 g/L; transfusion indicated.)	Interrupt everolimus until resolution to \leq Grade 1 or baseline value. If AE resolution occurs \leq 7 days, reintroduce everolimus at the same dose level. If AE resolution occurs $>$ 7 days, or event occurs within 28 days, reintroduce everolimus at one dose level lower, if available.
Grade 4 Neutropenia (neutrophils $<0.5 \times 10^9/L$) or Grade 4 anemia (Life-threatening consequences; urgent intervention indicated.)	Interrupt everolimus until recovery to \leq Grade 1 or baseline value. Reintroduce everolimus at one dose level lower, if available.*
Febrile Neutropenia	Interrupt everolimus until resolution to \leq Grade 1 (or baseline value) and no fever. Reintroduce everolimus at one dose level lower, if available.*
Grade 3 AE recurrence after dose reduction	Interrupt everolimus until resolution to \leq Grade 1. Reduce dose to the next lower dose level, if available. The lowest possible dose level of everolimus is 5 mg every other day (2.5 mg daily). Below this level, everolimus must be discontinued.

*Grade 4 AE recurrence (including febrile neutropenia) after dose reduction, discontinue everolimus.

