Patients in this study will be routinely questioned as to the presence of new or changed pulmonary symptoms consistent with pneumonitis. Moreover, potential lung radiological changes can be detected by the chest CT/MRI scans that are performed on all patients every 2 cycles for tumor assessment according to the schedule of events (Appendix D). Pulmonary function tests (PFTs) will be conducted, if clinically indicated, to monitor for pneumonitis. If non-infectious pneumonitis develops, the guidelines in Table 5 should be followed. Consultation with a pulmonologist is recommended for any case of pneumonitis that develops during the study.

CONFIDENTIAL

STUDY DRUG(S): EVEROLIMUS
FINAL PROTOCOL DATE: 19 JUNE 2014

SCRI INNOVATIONS STUDY NUMBER: BRE 212
VERSION 1.0

Table 5 Management of Non-Infectious Pneumonitis Due to Everolimus

Worst Grade Pneumonitis	Required Investigations	Management of Pneumonitis	Everolimus Dose Adjustment
Grade 1 (Asymptomatic, radiographic findings only)	CT scans with lung windows. Consider room air O ₂ saturation at rest	No specific therapy is required	Administer 100% of everolimus dose. Initiate appropriate monitoring.
Grade 2 (Symptomatic, not interfering with Activities of Daily Living)	CT scan with lung windows. Consider pulmonary function testing including: spirometry, DLCO, and room air O ₂ saturation at rest. Consider a bronchoscopy with biopsy and/or BAL. Monitor at each visit until return to ≤ Grade 1. Return to initial monitoring frequency if no recurrence.	Symptomatic only. Consider corticosteroids and/or other supportive therapy if symptoms are troublesome.	Rule out infection and consider interruption of everolimus until symptoms improve to ≤ Grade 1. Re-introduce everolimus at one dose level lower. Discontinue everolimus if failure to recover within ≤ 28 days.

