10.2 Sample Size Considerations

Results from the recently published BOLERO-2 study reported a median PFS of 2.8 months (as assessed by the treating investigator) that improved to 6.9 months as a result of the addition of everolimus in patients treated with exemestane after failing the NSAI therapy (Baselga J. et al. 2012). A similar median PFS is predicted in this study’s patient population that is based on similar inclusion criteria. It is anticipated that everolimus in combination with the last anti-estrogen therapy on which the patient demonstrated disease progression, will result in an increase in median PFS from 2.8 months to 5 months in this refractory population.

Based on the above assumptions, given a follow-up period of 12 months after the completion of enrollment (18 months), with a 5% alpha and a one-sided test of hypothesis, a sample size of 42 will provide 80% power to detect an improvement in median PFS from 2.8 months to 5 months in the patients treated with the combination of everolimus with anti-estrogen therapy. Allowing for 8-10% inevaluable patients, the total number of patients to be enrolled is 46 patients.

Sample size calculations are based on SWOGSTAT online sample size calculator for one-arm non-parametric survival endpoints (http://www.swogstat.org/stat/public/one_nonparametric_survival.htm).

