Appendix D: Schedule of Assessments (continued)

- a The physical examination including neurological examination, update of medical history, ECOG PS, CBC, CMP plus uric acid, magnesium, phosphorus, and PT or INR, PTT must be done \leq 7 days prior to initiation of treatment. However, if these initial examinations are obtained within 72 hours of Cycle 1 Day 1 they do not have to be repeated. Scans to document measurable or evaluable disease (i.e., tumor measurement) must be performed \leq 4 weeks prior to initiation of treatment.
- b Physical examination will include measurements of height (to calculate body surface area [BSA]), weight, and vital signs (resting heart rate, blood pressure, respiratory rate, oral temperature) at the Pre-Treatment Visit. Physical examinations (PE) done at all other times during the study will include only measurements of vital signs and weight.
- c Study drug compliance will be assessed at each patient visit. The study staff will count and document the amount of study drug taken and returned by the patient.
- d CMP will include measurements of glucose, BUN, creatinine, sodium, potassium, chloride, calcium, CO₂, alkaline phosphatase, AST, ALT, total bilirubin, total protein, and albumin.
- e Patients must fast at least 8 hours overnight prior to collection of the blood specimen.
- f Cholesterol/HDL/LDL/triglycerides do not need to be repeated on Cycle 1 Day 1 if they are normal at baseline. Repeat on Day 1 of every odd cycle.
- g If PT or INR, and PTT are normal at baseline they do not need to be repeated. Patients requiring the initiation of an anti-coagulation therapy during study treatment should have their coagulation test performed as clinically indicated.
- h A serum pregnancy test for all pre/peri menopausal women (regardless of ovarian suppression) is required at baseline \leq 7 days prior to date of first treatment. All pre/peri menopausal women will need a serum or urine pregnancy test every 2 cycles (8 weeks) before receiving study treatment. If a urine pregnancy test is positive, it must be followed by a serum pregnancy test.
- i Tumor specimens from the primary site or from metastatic lesions will be collected from all patients with available archived tissue. See lab manual for details.
- j Scans are required every 2 cycles, prior to the start of odd-numbered cycles beginning with Cycle 3. Bone scans that are abnormal at baseline must be repeated at restaging.

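### Restaging is scheduled by cycle count with no calendar anchor or scan window, so a toxicity hold can move the scan that dates progression

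*Protocol*

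**What the plan says.** Four places set the scan schedule, and three of them count cycles only.

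- Protocol 7.4: "Patients will be reevaluated for response to treatment after every 2 cycles of treatment, prior to the start of odd-numbered cycles".
- Protocol Appendix D, footnote j: "Scans are required every 2 cycles, prior to the start of odd-numbered cycles beginning with Cycle 3". The first restaging CT is also listed as a Cycle 3 Day 1 assessment in 7.3.2.
- SAP section 4, Efficacy Assessment Timepoints, repeats the rule in 7.4.
- Protocol 5.1.1, Restaging, alone adds a duration: a cycle is 4 weeks, "with radiological evaluations every 2 cycles (8 weeks").

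Other provisions allow treatment to be delayed. Section 6.1 says "Treatment on Day 1 of any cycle will proceed if blood counts demonstrate ANC" and platelets are at or above stated thresholds. The note to Table 2 allows an everolimus interruption of up to 28 days, Table 4 does the same, and Table 5 says "Discontinue everolimus if failure to recover within" 28 days. Section 6.3 allows the anti-estrogen to be stopped for up to 2 weeks.

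The SAP's PFS table dates progression at the first assessment that shows it. Section 2.4 makes the proportions progression-free at 4 and 6 months secondary endpoints.

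**The concern.** In a single-arm trial no control group shares the same scan delay. The PFS result is read against an external median of 2.8 months (Protocol 10.2). If a held cycle also holds the scan, a patient whose tumour has already grown stays progression-free on paper until the later scan. The timing of the primary endpoint would then depend partly on tolerability, and partly on how each of about nine sites reads the schedule.

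The two landmark rates are the most exposed. The week-16 and week-24 scans fall shortly before months 4 and 6, so a modest shift can carry a scan past the landmark.

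**Working it through.** **The plan's own figure.** Section 10.2 states "with a 5% alpha and a one-sided test of hypothesis, a sample size of 42 will provide 80% power" for an "increase in median PFS from 2.8 months to 5 months in this refractory population". Testing survival at the null median gives S0 = 0.50 and S1 = 0.5^(2.8/5) = 0.678. Then n = (1.645 + 0.842)² × S1(1 − S1)/(S1 − S0)² = 42.4, and power at n = 42 is 79.6%. The figure reproduces, and 42/0.92 gives 46 enrolled. Scan timing does not enter this calculation, so N is unaffected.

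**Scan dates on an undelayed grid.** At 52.18/12 = 4.348 weeks per month:

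- Weeks 8, 16 and 24 are 1.84, 3.68 and 5.52 months.
- Month 4 is week 17.39, so the week-16 scan precedes it by 1.39 weeks (9.7 days).
- Month 6 is week 26.09, so the week-24 scan precedes it by 2.09 weeks (14.6 days).
- A full 28-day hold before the first scan would move it from week 8 to week 12 (2.76 months).

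**Why the direction depends on the length of the shift.** With exponential PFS, the recorded rate at a landmark is true survival at the last scan before it, S(t) = 0.5^(t/median). For one patient's 4-month status:

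| Scans (weeks) | Last scan before month 4 | Rate, true median 2.8 | Rate, true median 5 |
|---|---|---|---|
| 8, 16 | week 16 | 40.2% | 60.0% |
| 9, 17 (1-week hold) | week 17 | 38.0% | 58.2% |
| 10, 18 (2-week hold before first scan) | week 10 | 56.6% | 72.7% |

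A shift shorter than the gap moves the scan closer to the landmark and lowers the rate slightly. A shift longer than the gap removes that scan and raises the rate. The same holds at month 6 with the 14.6-day gap.

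**Size under assumed holds.** I simulated 1,000,000 exponential PFS times per setting, each dated at the first scan at or after it. Each 8-week interval was lengthened with probability p by a uniform 1–4 weeks. Both p and the hold length are assumptions.

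| True median | p | Recorded median (months) | 4-month rate | 6-month rate | Change in mean recorded PFS (months) | Recorded earlier than on fixed grid |
|---|---|---|---|---|---|---|
| 2.8 | 0 | 3.68 | 40.2% | 25.5% | – | – |
| 2.8 | 0.15 | 3.68 | 44.7% | 27.9% | +0.06 | 8.6% |
| 2.8 | 0.30 | 3.68 | 48.3% | 29.7% | +0.12 | 15.2% |
| 2.8 | 0.50 | 4.11 | 51.9% | 31.2% | +0.19 | 21.2% |
| 5 | 0 | 5.52 | 60.0% | 46.5% | – | – |
| 5 | 0.15 | 5.80 | 63.4% | 48.7% | +0.06 | 14.6% |
| 5 | 0.30 | 6.05 | 66.2% | 50.5% | +0.11 | 22.9% |
| 5 | 0.50 | 6.21 | 68.9% | 51.9% | +0.18 | 28.5% |

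The move from a true 2.8 to a recorded 3.68 months comes from the 8-week grid itself and is not an effect of holds.

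With 1-week holds only, in 15% of intervals, the 4-month rate is flat (40.1% against 40.3%; 59.9% against 60.0%) and the 6-month rate is about half a point lower.

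For scale, the binomial standard error of a 60% rate in 42 patients is √(0.6 × 0.4/42) = 7.6 points. The 4-month shifts of 3.4 to 11.7 points are about 0.4 to 1.5 standard errors.

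The model dates every event at a scan. Deaths without prior progression, and progression documented between scheduled visits, are dated when they occur and would dilute these effects.

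**The case against.** The strongest reply is that the plan already implies a calendar schedule. A cycle is defined by its length, 4 weeks, and 5.1.1 writes the scan interval as 8 weeks. Everolimus is taken continuously, and staff record missed doses at Day 1 of each cycle, so a cycle can contain missed doses. Section 6 keeps the anti-estrogen on schedule while everolimus is held. Tables 2 to 5 interrupt the drug and not the cycle. Section 6.1 conditions treatment on blood counts only and does not say that the visit, the cycle number or the scan moves.

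This stands to the extent that a reader might infer that the protocol makes toxicity postpone the scan, and no passage says so. A postponed scan is a permitted reading and not a stated rule. It does not remove the problem. The 8-week remark does not address holds, the anti-estrogen sentence does not mention scans, and 7.4 and footnote j tie the scan to the start of the next odd cycle. Two sites could scan the same patient at week 8 and at week 12, and each could point to the text.

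A reader might also infer that delay can only lengthen recorded PFS. That is false. Progression at week 17 is recorded at week 24 on the fixed grid, but at week 18 after a 2-week shift. In the simulation 9–29% of patients have an earlier recorded date than on the fixed grid.

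Finally, the hold frequency has no source in the documents. The Grade 3–4 event rates quoted in section 1.2 (3–8% per event type) are not rates of holds per interval. The toxicity-dependent interval that the protocol does state is a different one: follow-up every 3 months ± 1 month after stopping treatment before progression (7.6.1).

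**Conclusion.** The gap is real. Scans follow cycle numbers, treatment at cycle start can be held, and neither document says what happens to the scan or gives a window. Assessment timing can therefore vary with toxicity and with site practice in a trial whose primary endpoint is dated by scan.

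If sites do let scans slip, recorded PFS lengthens on average, but only slightly: about 0.06–0.2 months in the mean under the assumed holds. The recorded median moves from 5.5 to 5.8–6.2 months at a true median of 5. At 2.8 it stays at 3.68 until holds reach about half of intervals, then becomes 4.1. The landmark rates are more sensitive. The 4-month rate rises by about 3–12 points and the 6-month rate by 2–6 points, but only where accumulated shifts exceed about 10 and 15 days respectively.

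These figures rest on exponential PFS, 1–4 week holds in 15–50% of intervals, and every hold moving the scan. The documents supply none of these. They show what the ambiguity could cost and do not predict a bias in this trial. The change is worth making because it is nearly free and protects the primary endpoint.

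**What to change.** Make Protocol 5.1.1 (Restaging), 7.4 and Appendix D footnote j, and SAP section 4, say the same thing: tumour assessments (CT, and bone scan if abnormal at baseline) occur every 8 weeks by calendar from Cycle 1 Day 1, within a stated window such as ± 7 days, regardless of dose holds or cycle delays. The Cycle 3 Day 1 listing in 7.3.2 and the Appendix D table should refer to that rule.

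The cost is about one sentence in each place and an occasional extra scan for a patient whose cycle is delayed. It matches the 8-week interval already written in 5.1.1. No dose or treatment rule changes, and the sample size stays at 42 evaluable and 46 enrolled.

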7.5 End of Study Treatment

The follow-up evaluations required after treatment ends (due to disease progression, or once the patient is discontinued due to unacceptable toxicity or decision to discontinue treatment by the patient or the study physician) are specified in Appendix D. **A blood sample for the VeriStrat® assay will be collected from patients at the time of disease progression.**

After withdrawal from protocol treatment, patients must be followed for adverse events for 30 calendar days after the last dose of study drug. The following assessments will be performed for the End of Study Treatment Visit:

- Update of medical history
- PE including measurement of weight and vital signs
- ECOG PS (See Appendix A)
- AE assessment
- Concomitant medication review
- Study drug compliance assessment
- CBC, including 3-part differential and platelets
- CMP
- Fasting serum glucose
- Cholesterol, HDL, LDL, and triglycerides
- Serum or urine pregnancy test for all pre/peri menopausal women (regardless of ovarian suppression). If a urine pregnancy test is positive, it must be followed by a serum pregnancy test.
- CT scan of chest, abdomen and pelvis
- Blood sample for the VeriStrat® assay (only if patient is discontinued due to disease progression)

CONFIDENTIAL

STUDY DRUG(S): EVEROLIMUS
FINAL PROTOCOL DATE: 19 JUNE 2014

SCRI INNOVATIONS STUDY NUMBER: BRE 212
VERSION 1.0

7.6 Follow-up

7.6.1 Follow-up for Patients Who Discontinue Prior to Disease Progression

Patients who discontinue study treatment prior to the occurrence of disease progression will be followed every 3 months (\pm 1 month) from the date of last dose of study drug until disease progression or for up to 3 years from the start of treatment whichever comes first. Assessments at these visits will be performed as described in Appendix D. **A VeriStrat serum sample will be collected from all patients at the time of disease progression.**

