- k After patients complete therapy or are discontinued from the study, they will visit the study center 30 days after finishing treatment for end-of-treatment assessments. CT scans performed within 8 weeks prior to the End of Treatment visit do not need to be repeated. All patients will be followed during the off study period until all treatment related toxicity resolves, and for at least 30 days post-study drug discontinuation.
- l Patients who discontinue study treatment prior to the occurrence of disease progression will be followed every 3 months (\pm 1 month) from the date of last dose of study drug until disease progression or for up to 3 years whichever comes first. A blood sample will be collected for the VeriStrat[®] assay at disease progression.
- m Patients will be followed for survival status after study treatment has ended (including the discontinuation of treatment for any reason prior to the end of the study) every 3 months (\pm 1 month) for up to 3 years or until patient death whichever comes first. A blood sample will be collected for the VeriStrat[®] assay at the 1st follow-up visit after disease progression. For subsequent follow-up visits, patients may be contacted during outpatient visits or by telephone.
- n Blood samples will be collected from all patients enrolled on the study for the VeriStrat[®] assay. Samples will be collected at baseline, prior to start of treatment on C3D1, at disease progression and at the 1st follow-up visit after disease progression.
- o HBV-DNA, HBsAg, HBcAb, HBsAb and/or HCV RNA testing applies only to patients at risk for hepatitis (Section 7.1)

CONFIDENTIAL

STUDY DRUG(S): EVEROLIMUS
FINAL PROTOCOL DATE: 19 JUNE 2014

SCRI INNOVATIONS STUDY NUMBER: BRE 212
VERSION 1.0

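### After an early stop, scans move from every 8 weeks to every 3 months (±1 month), so PFS is either dated late (Protocol rule) or possibly informatively censored (SAP rule) in the same patients; the plan should settle which and add one sensitivity row.

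*Protocol*

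**What the plan says.** - **On treatment.** Protocol 5.1.1 (Restaging) and 7.4 set CT every two 4-week cycles, i.e. every 8 weeks.
- **After a stop without progression.** Protocol 7.6.1: "Patients who discontinue study treatment prior to the occurrence of disease progression will be followed every 3 months". The window is ±1 month and visits are counted from the last dose. Appendix D marks CT at these visits, and SAP section 4 repeats the schedule.
- **End of Treatment.** Appendix D footnote k puts this visit 30 days after treatment ends and adds: "CT scans performed within 8 weeks prior to the End of Treatment visit do not need to be repeated". Protocol 7.5 lists the CT without the waiver but refers to Appendix D.
- **PFS rule, Protocol 10.4.2.** Stopping treatment is not a reason for censoring. Patients are censored at the last assessment if they are event-free, or at the last assessment before any new anticancer therapy.
- **PFS rule, SAP section 4.** The event table has a separate row that censors, at the last evaluable assessment, patients who stop because of toxicity or another cause that is not an endpoint.
- **Partial stop.** Protocol section 6 keeps patients who stop everolimus on anti-estrogen therapy if they benefit. Protocol 11.1.5 calls everolimus the study treatment. Neither says which scan schedule then applies.

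**The concern.** Under the Protocol rule, how soon a progression is found depends on whether the patient has stayed on treatment. The trial has one arm, and PFS is read against a fixed 2.8-month median, so nothing on a comparator side offsets the looser schedule. Later detection can raise the 4- and 6-month progression-free rates, which are named secondary endpoints, and it exposes the criterion of stable disease for 6 months to the same delay.

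Under the SAP row, read literally, those progressions are not events at all. Patients who stop then leave the risk set at their last scan, which is harmless only if their prognosis matches that of patients who continue. The two documents thus give different answers for the same patients, and no planned sensitivity analysis addresses assessment timing.

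**Working it through.** **1. The plan's own figure.** Protocol 10.2: "with a 5% alpha and a one-sided test of hypothesis, a sample size of 42 will provide 80% power", for an "increase in median PFS from 2.8 months to 5 months in this refractory population". Test survival at 2.8 months, with variance under the alternative:
- S0 = 0.50; S1 = 2^(−2.8/5) = 0.678.
- n = (1.645 + 0.842)² × 0.678 × 0.322 / (0.178)² ≈ 42.4; power at 42 is 79.6%.
- Enrolled: 42/0.92 = 45.7, so 46; 42/0.90 = 46.7, so 47. The plan says 46.

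The sample size reproduces, and the scan schedule does not contradict it.

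**2. Scan gaps** (1 month = 30.44 days)
- On treatment: 56 days = 1.84 months.
- A waived CT can be up to 56 − 30 = 26 days before the last dose.
- The first follow-up scan can be 4 months after the last dose = 121.75 days.
- Largest first gap: 26 + 121.75 = 147.75 days = 4.85 months. With an on-time visit: 26 + 91.3 = 117.3 days = 3.85 months.
- If the End of Treatment CT is done on day 30: 121.75 − 30 = 91.75 days = 3.0 months.
- Later visits, windows anchored to last dose: month 2 to month 7 = 5.0 months. If each window runs from the previous visit, later gaps are at most 4 months.

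**3. Why the median is hard to move.** With 8-week scans and exponential PFS, the Kaplan-Meier curve steps only at scan dates.
- True median 2.8: 2^(−1.84/2.8) = 63% after the day-56 scan, 2^(−3.68/2.8) = 40% after day 112, 2^(−5.52/2.8) = 25% after day 168. The estimated median is 3.68 months.
- True median 5: 77%, 60% and 47%. The estimated median is 5.52 months.

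A modest number of late-dated events rarely carries the curve past a step.

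**4. Simulation under Protocol 10.4.2.** Exponential PFS and random stopping. The documents give no stop rate, so 15%, 25% and 35% are assumptions. True median 2.8 months, progression-free %:

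| | 8-week scans | 15% stop | 25% stop | 35% stop |
|---|---|---|---|---|
| 4 months, run 1 | 40 | 42 | 43 | 44 |
| 4 months, run 2 | 40 | 42 | 44 | 46 |
| 6 months, run 1 | 25 | 27 | 28 | 29–30 |
| 6 months, run 2 | 25 | 27 | 29 | 30 |

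At true median 5 the rise is 1–2 points (run 1) or 1–3 (run 2). A third run gave 0.5–3 points overall. Mean detection delay in patients who stop goes from 4.0 weeks to 6.4–6.9 weeks, with 9–11% above 13 weeks.

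A separate run had 10–30% of patients assigned a stop time between days 28 and 120. The large-sample median stayed at 3.68 or 5.52 months in every scenario but one: true median 5, 30% stops, all visits a month late, where it went from 5.52 to 5.98. The proportion beyond 2.8 months was not raised (true median 2.8, 30% stops: 63.4% with 8-week scans, 62.8% under the Protocol). At n = 46, run 1 found a later median than under 8-week scans in 6–28% of trials.

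**5. Dependence on when patients stop.** Take a stop just after a clear day-56 scan. The End of Treatment CT is waived, and the next on-time scan is day 56 + 91 = 147, beyond 4 months (day 122). That patient counts as progression-free at 4 months with certainty, against 63% under 8-week scans (true median 2.8). If every stop fell there, 15% stopping would add 0.15 × 37 = 5.5 points and 35% would add 0.35 × 37 = 13. This is an upper limit, not an expectation.

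**6. Under the SAP row.** With stopping independent of prognosis, censoring at the last scan left the median at 3.68 or 5.52 months. That run cannot show bias from informative stopping, because it assumes there is none.

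**The case against.** The strongest objection is the SAP row. A reader might infer that PFS is simply lengthened in patients who stop for toxicity. The documents do not support that without qualification: if the row applies as written, a later progression is not an event and cannot be dated late. The row could cover only patients with no later event, but the table already has a row for patients with neither progression nor death, so the narrower reading makes it redundant. This objection stands, and it changes the nature of the problem rather than removing it.

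Other limits also stand:
- Patients who start new therapy before progression are censored beforehand.
- Patients without one full cycle and a post-baseline assessment are outside the primary population.
- The SAP allows for progression documented between scheduled visits.
- Footnote k permits omission of the End of Treatment CT; it does not require it.
- Patients who continue anti-estrogen therapy may stay on 8-week scans.

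The effect is also small beside sampling error: at n = 46 the 95% half-width around 40% is 1.96 × √(0.40 × 0.60/46) ≈ 14 points. That does not dispose of the point, because this is a shift in one direction that the confidence interval does not reflect. Finally, it is tempting to set 4.9 months against the targeted gain of 5 − 2.8 = 2.2 months. That compares one patient's worst case with a difference in medians; the typical added delay is about 2.4 to 2.9 weeks.

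**Conclusion.** The point holds in a limited form. The change of schedule and the waiver are plain in the text, and the first post-treatment gap can reach about 4.9 months (5.0 between later visits if windows are anchored to the last dose).

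If Protocol 10.4.2 governs, the 4- and 6-month rates rise by roughly 0.5 to 4 points in most runs at assumed stop rates of 15–35%. The largest figure is 6 points, and stops clustered soon after a scan could add more. Stable disease for 6 months is exposed to the same delay, though its size was not computed. If the SAP row removes later progressions, the concern is potentially informative censoring, whose size and direction the documents do not allow one to estimate.

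A reader might infer that the primary median is materially biased toward benefit, or that poorer tolerability always means more bias. Neither follows: the large-sample median moved in only one of the re-derived scenarios, and the earliest stops fall outside the primary population. The sizes rest on exponential PFS, random stopping and stop rates that the documents do not give.

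**What to change.** This is a cheap improvement to the wording and the analysis:

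1. **Reconcile Protocol 10.4.2 with the SAP section 4 PFS table.** State that stopping treatment does not by itself censor, and that progression or death before subsequent therapy is an event. Limit the SAP discontinuation row to patients with no later event.
2. **Add a PFS sensitivity row to SAP Table 8, including the 4- and 6-month rates.** Date a progression first found on the post-treatment 3-monthly schedule to the first missed 8-week timepoint after the last clear scan, or keep the scan date if that is earlier. This is the early extreme and the Protocol 10.4.2 estimate the late one, so together they bracket the landmark rates that 8-week scanning would give.
3. **State which scan schedule applies** when everolimus stops and anti-estrogen therapy continues.

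The cost is SAP and protocol wording, a little programming, and a slightly shorter PFS in the added row. Keeping 8-week imaging after a stop would remove the problem at source, but it needs an amendment and about 15 extra CTs (1–2 per patient, if 25% of 46 stop), so it is optional.
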